### Venous thromboembolism assessment

In case of suspected recurrent VTE, the event should be evaluated using appropriate imaging modalities per local guidelines or as required per investigator judgment. Example of appropriate evaluations methods are listed below.

- Suspected DVT: Venous compression ultrasonography (CUS) or venography
- Suspected PE: Ventilation-perfusion (V-Q) lung scan, pulmonary angiography or spiral (helical) CT
- Suspected paradoxical embolism (PDE): CT/MR angiography or other appropriate evaluation

### Bleeding assessment

#### Patients will be carefully assessed for signs and symptoms of bleeding

The following definitions for bleeding are based on recommendations made by the Perinatal and Paediatric Haemostasis Subcommittee during the 56th-58th Scientific and Standardization Committee (SSC) Meetings of the ISTH ([R11-4225](#)).

#### Major bleeding:

- Fatal Bleeding
- Clinically overt bleeding associated with a decrease in haemoglobin of at least 2 g/dL (20 g/L) in a 24 hour period
- Bleeding that is retroperitoneal, pulmonary, intracranial, or otherwise involves the central nervous system
- Bleeding that requires surgical intervention in an operating suite

#### Clinically relevant non-major (CRNM) bleeding:

- Overt bleeding for which a blood product is administered and which is not directly attributable to the patient's underlying medical condition
- Bleeding that requires medical or surgical intervention to restore haemostasis, other than in an operating suite.

#### Minor bleeding:

- Minor bleeds are any overt or macroscopic evidence of bleeding that does not fulfil the criteria for either major bleeding or clinically relevant, non-major bleeding.

## 5.2.2 Assessment of adverse events

### 5.2.2.1 Definitions of adverse events

#### Adverse event

An adverse event (AE) is defined as any untoward medical occurrence, including an exacerbation of a pre-existing condition, in a patient or clinical investigation subject who received a pharmaceutical product. The event does not necessarily have to have a causal relationship with this treatment.

#### Serious adverse event

A serious adverse event (SAE) is defined as any AE which results in death, is immediately life-threatening, results in persistent or significant disability / incapacity, requires or prolongs patient hospitalisation, is a congenital anomaly / birth defect, or is to be deemed serious for any other reason if it is an important medical event when based upon appropriate medical judgment which may jeopardise the patient and may require medical or surgical intervention to prevent one of the other outcomes listed in the above definitions.

#### Intensity of adverse event

The intensity of the AE should be judged based on the following:

- Mild: Awareness of sign(s) or symptom(s) which is / are easily tolerated  
Moderate: Enough discomfort to cause interference with usual activity  
Severe: Incapacitating or causing inability to work or to perform usual activities

#### Causal relationship of adverse event

Medical judgment should be used to determine the relationship, considering all relevant factors, including pattern of reaction, temporal relationship, de-challenge or re-challenge, confounding factors such as concomitant medication, concomitant diseases and relevant history. Assessment of causal relationship should be recorded in the case report forms.

- Yes: There is a reasonable causal relationship between the investigational product administered and the AE.  
No: There is no reasonable causal relationship between the investigational product administered and the AE.

#### Worsening of the underlying disease or other pre-existing conditions

Worsening of the underlying disease or of other pre-existing conditions will be recorded as an (S)AE in the (e)CRF.

### Changes in vital signs, ECG, physical examination, and laboratory test results

Changes in vital signs, ECG, physical examination and laboratory test results will be recorded as an (S)AE in the (e)CRF, if they are judged clinically relevant by the investigator.

### Protocol-specified Adverse Events of Special Interest (AESI)

The following are considered as Protocol-specified AESI:

- Hepatic injury defined by the following alterations of liver parameters: An elevation of AST and / or ALT  $\geq 3$  fold ULN combined with an elevation of total bilirubin  $\geq 2$  fold ULN measured in the same blood draw sample. Patients showing these lab abnormalities need to be followed up according to [Appendix 10.2](#) of this clinical trial protocol and the “DILI checklist” provided in ISF/RDC.
- Creatinine value shows a  $\geq 2$  fold increase from baseline and is above the upper limit of normal.

Protocol-specified AESI are to be reported in an expedited manner similar to Serious Adverse Events, even if they do not meet any of the seriousness criteria – for details please see [Section 5.2.2.2](#).

#### 5.2.2.2 Adverse event and serious adverse event reporting

All adverse events, serious and non-serious, occurring during the course of the clinical trial (i.e., from signing the informed consent until end of follow-up period) will be collected, documented and reported to the Sponsor by the investigator on the appropriate CRF(s)/eCRFs/SAE reporting forms. The investigator does not need to actively monitor patients for adverse events once the clinical trial has ended. However, if the investigator becomes aware of an SAE(s) that occurred after the patient has completed the clinical trial (including any protocol required residual effect period (REP) and / or follow-up), it should be reported by the investigator to the Sponsor if considered relevant by the investigator. Reporting will be done according to the specific definitions and instructions detailed in the ‘Adverse Event Reporting’ section of the Investigator Site File.

The residual effect period (REP) for dabigatran is 3 days after last drug administration. Therefore all AEs reported within 3 days of the last trial medication will be considered on treatment. All AEs, including those persisting after trial completion must be followed up until they have resolved or have been sufficiently characterized.

For each adverse event, the investigator will provide the onset date, end date, intensity, treatment required, outcome, seriousness, and action taken with the investigational drug. The investigator will determine the relationship of the investigational drug to all AEs as defined in [Section 5.2.2.1](#).

The investigator must report the following events using paper process SAE form via telephone / fax immediately (within 24 hours) to the Sponsor: SAEs, AESIs and non-serious AEs relevant to the SAE and / or AESI.

**Proprietary confidential information.**

© 2019 Boehringer Ingelheim International GmbH or one or more of its affiliated companies. All rights reserved.

This document may not - in full or in part - be passed on, reproduced, published or otherwise used without prior written permission.

BI has set up a list of AEs which are defined to be always serious. In order to support the investigator with the identification of these “always serious adverse events”, if a non-serious AE is identified to be serious per BI definition, a query will be raised. The investigator must verify the description and seriousness of the event. If the event description is correct, the item “serious” needs to be ticked and an SAE has to be reported in expedited fashion following the same procedure as above.

The list of these adverse events can be found via the RDC-system.

The SAE form is to be forwarded to the defined unique entry point identified for the BI OPU (country-specific contact details will be provided in the Investigator Site File). This immediate report is required irrespective of whether the investigational product has been administered or not and irrespective of causal relationship. It also applies if new information to existing SAEs or protocol-specified AESI becomes available.

## Pregnancy

In rare cases, pregnancy might occur in clinical trials. Once a female subject has been enrolled into the clinical trial, after having taken study medication, the investigator must report immediately any drug exposure during pregnancy to the Sponsor. Drug exposure during pregnancy has to be reported immediately (within 24 hours) to the defined unique entry point for SAE forms of the respective BI operative unit (country-specific contact details will be provided in the Investigator Site File). The outcome of the pregnancy associated with the drug exposure during pregnancy must be followed up. In the absence of an (S)AE, only the Pregnancy Monitoring Form for Clinical Trials and not the SAE form is to be completed. The ISF will contain the Pregnancy Monitoring Form for Clinical Trials (Part A and Part B).

### **5.2.3 Assessment of safety laboratory parameters**

A central laboratory will be used for the analysis of all laboratory measurements with the exception of serum or urine pregnancy test, INR, serum creatinine, HCT, Hb, Platelet count, ALT and AST measurement at screening (if applicable) which may be done locally to facilitate the eligibility assessment. If needed and when feasible a local laboratory may alternatively be used for dTT testing to evaluate dabigatran concentration. Local lab assessments are also acceptable in emergency situations (e.g. bleeding event or emergency surgery), see [Appendix 10.1](#).

Refer to the [Flow Chart](#) and [Section 5.7.2](#) for additional information.

For patients who have completed the treatment period of study 1160.106, the lab results from Visit 8 will be taken as Visit 1 or Visit 2 results of this trial, depending on the day Visit 1 and Visit 2 take place in correlation to Visit 8 of study 1160.106 (see [Flow Chart](#), Footnotes 1 and 2).

A centralized serum pregnancy test for females who have reached menarche will be done as noted in the Flow Chart.

### **5.2.4 Electrocardiogram**

An ECG will be done at screening and all other time points as noted in the Flow Chart. Documentation of, and findings from ECGs, must be part of the source documents available at the site.

Printed paper tracings from 12-lead ECGs (I, II, III, aVR, aVL, aVF, V1-V6) will be collected and stored at the site. In the event of any cardiac symptoms or ECG abnormalities (i.e. heart rhythm disorders, PR prolongation, QRS enlargement, QT prolongation, etc.), additional ECGs will be recorded at investigator discretion. All ECGs will be evaluated (signed, dated and commented upon) by the treating physician / investigator and stored locally. Any clinically relevant changes (according to investigators judgment) in the ECG will be reported as AEs and followed up and / or treated locally until a normal or stable condition if feasible is achieved.

**Proprietary confidential information.**

© 2019 Boehringer Ingelheim International GmbH or one or more of its affiliated companies. All rights reserved.

This document may not - in full or in part - be passed on, reproduced, published or otherwise used without prior written permission.

All ECGs performed at any time during the conduct of the trial (whether clinically relevant or routine) will be stored in the subject source notes.

### **5.2.5 Assessment of other safety parameters**

#### **5.2.5.1 Vital signs**

Blood pressure (BP) and heart rate (HR) will be performed at the time points noted in the [Flow Chart](#). For each patient, all BP recordings shall be made using preferably the same type of instrument on the same arm during the entire course of the study.

#### **5.2.5.2 Weight assessment**

Weight measurements should preferably be done on the same age-appropriate scale. In order to get comparable body weight values, weight measurements should be performed in the following way:

- shoes and coats / jackets should be taken off (when applicable)
- pockets should be emptied of heavy objects (i.e. keys, coins etc.) when applicable

### **5.3.2 Other assessments**

- Incidence of adverse events, protocol-specified AESI and serious adverse events
- 

#### 5.4 APPROPRIATENESS OF MEASUREMENTS

All safety and clinical assessments are determined using standard methods and procedures.

## 5.6 BIOMARKER(S)

Please refer to Section 5.7.

## 5.7 PHARMACODYNAMICS

### 5.7.1 Pharmacodynamic endpoints

Determination of the exploratory pharmacodynamic parameters dTT (Anti-Factor IIa activity), aPTT and ECT will be performed in this trial. Diluted thrombin time (dTT) or alternative registered method / assay (where available and after consultation of the Sponsor) will be employed for the quantitative measurement of dabigatran concentrations for dose adjustment. The analysis of dTT will be done by a central laboratory. Diluted TT may also be analysed by a local laboratory, if feasible. The dabigatran etexilate dose administered to patients may be adjusted upon dabigatran plasma level measurement from Visit 3 or other future visits as needed to achieve the target plasma range, based on the assessment of dabigatran plasma levels. Further, alternative coagulation assays for dabigatran, e.g. ecarin based tests, may be explored.

### 5.7.2 Methods of sample collection

About 22.8 mL of blood (approximately 2.4 mL per sampling time point) in total per patient assigned to dabigatran etexilate is planned for collection for the PD samples.

The collection time point for aPTT, ECT and dTT (Anti-Factor IIa activity) (or alternative method) are indicated in the [Flow Chart](#). The date and exact clock time of when these PD samples are taken is to be recorded in the eCRF. Further, the date and the exact clock time of dabigatran etexilate administration on the three days before the PD samples are taken is to be recorded in the eCRF. The PD samples should be taken immediately after the PK samples have been obtained. To ensure correct identification and tracking of the PD samples, all sample tubes will be labelled with trial number, patient number and day and exact time of sample collection.

## 6. INVESTIGATIONAL PLAN

### 6.1 VISIT SCHEDULE

The trial consists of three periods, a screening period, an open-label dabigatran etexilate treatment period and a follow-up period.

The schedule for trial visits is summarised in the study [Flow Chart](#) including time windows for study visits. All visit dates are calculated from the date of treatment assignment (Visit 2). In the event that visits are missed or out of sequence, subsequent visits will be planned according to the date of Visit 2.

### 6.2 DETAILS OF TRIAL PROCEDURES AT SELECTED VISITS

No study procedures may be initiated prior to the patient's parents (or legal guardian) signing the informed consent and the patient providing assent (if applicable) in compliance with ICH-GCP and local legislation.

#### 6.2.1 Screening period

For the schedule of assessments and procedures to be done during screening refer to the [Flow Chart](#). In addition:

- Document consenting procedure (and assenting if applicable) in the patient's source file.
- Record enrolment (date of patient consent) on the enrolment log (located in the Investigator Site File).

For patients participating in study 1160.106 the Screening Visit may be conducted together with Visit 8 of 1160.106 trial.

#### 6.2.2 Treatment period

Before giving the first dose of study medication, eligibility must be confirmed.

For the schedule of assessments and procedures during the treatment period refer to the Flow Chart. For information on dose selection and drug assignment and administration refer to [Section 4.1.3](#) and [Section 4.1.4](#). For details PD sample collection and analyses refer to [Section 5.7](#).

Visit 3 is not applicable for patients who have previously completed the treatment period of the 1160.106 study being on dabigatran etexilate and continue taking the same dose in this trial. For all other patients, during Visit 3 the trough dabigatran concentration will be determined

ensure maintenance within a 50 to < 250 ng/mL window. If target exposure of 50 to < 250 ng/mL is not achieved an Unscheduled Visit must be performed in order to adjust the dabigatran etexilate dose (refer to

**Proprietary confidential information.**

© 2019 Boehringer Ingelheim International GmbH or one or more of its affiliated companies. All rights reserved.

This document may not - in full or in part - be passed on, reproduced, published or otherwise used without prior written permission.

[Appendix 10.4.2](#)). A Titration Visit must be scheduled preferably after 3 days have elapsed (or 6 new doses have been taken) after a dose adjustment to reassess if the new trough dabigatran concentration is within the target range. Patients must not be dosed at home prior to attending a Titration Visit; dosing will be done after a trough plasma sample is collected. If patients cannot reach trough plasma concentrations between 50 and < 250 ng/mL after one dose adjustment, they must discontinue the study medication.

Unscheduled Visits are to be conducted in all cases of suspected recurrent VTE, paradoxical embolism (PDE), occurrence of post-thrombotic syndrome (PTS), major or clinically-relevant bleeding events (MBEs/CRBEs) or other suspected AESI or SAE. The Unscheduled Visit should be performed as soon as possible, preferably within 24 hours after the site first becomes aware of a suspected event.

### 6.2.3 End of trial and follow-up period

Follow-up Visit should be planned for 28 days after last drug intake. For the assessments and procedures to be done during the Follow-up Visit refer to the [Flow Chart](#).

All patients who prematurely discontinue treatment will be invited to perform an eEOT Visit. Subsequently they will be followed up according to the remaining visit schedule until the end of the study. At these visits collection of AEs, outcome events (e.g. occurrence of PTS, VTE, bleeding events, etc.) and use of concomitant medication will be made.

Patients that are not actively taking study drug and their parent/legal guardian may be less motivated to adhere to the study visit schedule. Investigator and site staff should work to detect early signs of losing interest and readily present such patients (not actively taking study drug) and their parent/legal guardian with the following opportunities to encourage continued participation:

- continue to attend regularly scheduled study visits until the trial ends
- conduct only the final visit in person. All other visits would be done over the phone.
- conduct all remaining study visits over the phone
- discontinue participation in remaining trial activities but permit collection of vital status and outcome events at the end of the trial.
- discontinue participation in remaining trial activities but permit collection of vital status at the end of the trial.

The patient / parent / legal guardian will be asked to choose the most rigorous follow-up they are willing to comply with.

For patients who completely withdraw consent no more data on their medical information will be requested.

The site must make periodic documented attempts (approximately every three months) to locate patients who are lost to follow up (LTFU).

## 7. STATISTICAL METHODS AND DETERMINATION OF SAMPLE SIZE

### 7.1 STATISTICAL DESIGN - MODEL

This trial has a single treatment group with no control group. Overall assessment of safety will be based on descriptive statistics.

### 7.2 NULL AND ALTERNATIVE HYPOTHESES

There is no hypothesis testing for this trial.

### 7.3 PLANNED ANALYSES

The primary analysis will include patients who were dispensed study medication and have received at least one dose of study medication (Treated set).

The analysis of the /PD parameters will be performed on Pharmacokinetic set (PKS). PKS will include all treated patients with at least one /PD measurement and having no protocol violations relevant to the evaluation of PD endpoints.

#### 7.3.1 Primary analyses

The primary analyses will be based on the primary safety endpoints. The recurrence of VTE, major bleeding events, minor (including clinically relevant non-major (CRNM)) bleeding events, overall mortality and mortality related to thromboembolic events will be analysed as time-to-event and will be summarized by Kaplan-Meier estimates. The rate of occurrence of events at 6 and 12 months will also be provided by K-M estimation. Patients who do not have any of the events or drop out early will be considered as censored for this analysis. Additionally, descriptive rate with number of patients with event divided by total treated patients will also be provided. Early drop out and lost-to-follow-up will be considered as non-event. The components of the composite event will be summarized as below:

- Recurrence of venous thromboembolism will be summarized by Kaplan-Meier estimate of time to first recurrence of VTE. The rate of recurrence at 6 and 12 months will also be provided by K-M estimation. Patients, who do not experience recurrent VTE by the time of analyses, drop out from the study, or die from non-VTE related cause will be considered as censored. The descriptive rate of number of patients with event divided by total treated patients will also be provided. Early drop out and lost-to-follow-up will be considered as non-event when calculating the descriptive rate.
- Major bleeding and minor (including clinically relevant non-major (CRNM)) bleeding will be analysed by K-M estimate of time to first occurrence as competing events. The K-M rate estimate at 6 and 12 month will be provided. The descriptive rate will also be calculated by dividing number of patients with major / minor bleeding by the number of total treated patients. Early drop out, lost-to-follow-up and non-bleeding related death will be considered as non-event and censored.

Proprietary confidential information.

© 2019 Boehringer Ingelheim International GmbH or one or more of its affiliated companies. All rights reserved.

This document may not - in full or in part - be passed on, reproduced, published or otherwise used without prior written permission.

- Mortality overall and related to thrombotic or thromboembolic event will be summarized separately by K-M estimate of time to death. The K-M rate and descriptive rate at 6 and 12 month will be calculated. Early drop out and lost-to-follow-up will be considered as non-event. Non-thrombotic or non-thromboembolic related death will be considered as censored case for mortality due to thrombotic or thromboembolic events.

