### 7.3.2 Secondary analyses

Secondary analyses are planned for occurrence of post-thrombotic syndrome (PTS), number of dabigatran etexilate dose adjustments (i.e. Number of patients with dabigatran dose adjustments) and pharmacodynamic assessments at Visit 3 (after at least six consecutive dabigatran etexilate doses) and after at least 3 days following any dabigatran etexilate dose adjustment.

- Occurrence of PTS will be summarized by K-M estimate of time to first occurrence. The K-M rate and descriptive rate at 6 and 12 month will be calculated. Early drop out, lost-to-follow-up and death will be considered as non-event and censored.
- Frequency of dabigatran etexilate dose adjustments will be summarized descriptively. This refers to the number of patients with dabigatran etexilate dose adjustment during treatment period because each patient is allowed to have only one dose adjustment.
- pharmacodynamic analyses details can be found in [Section 7.3.5](#) and [7.3.6](#).

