#### 7.4 HANDLING OF MISSING DATA

Missing data will not be imputed in general. All patients will be followed to collect necessary efficacy and safety information, even if patients discontinue study medication prematurely.

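### The supplementary descriptive rates in 7.3.1 and 7.3.2 count patients with unknown outcome as event-free, so they understate risk whenever follow-up is incomplete; the planned Kaplan-Meier rates do not share this fault

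*Protocol*

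**What the plan says.** Section 7.3.1 states that recurrent VTE, bleeding and mortality "will be analysed as time-to-event and will be summarized by Kaplan-Meier estimates". It adds that "The rate of occurrence of events at 6 and 12 months will also be provided by K-M estimation", and for this analysis "Patients who do not have any of the events or drop out early will be considered as censored for this analysis".

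A second figure follows: "Additionally, descriptive rate with number of patients with event divided by total treated patients will also be provided". The next sentence gives its counting rule: "Early drop out and lost-to-follow-up will be considered as non-event". The VTE bullet repeats the rule and ties it to this figure: "Early drop out and lost-to-follow-up will be considered as non-event when calculating the descriptive rate". The bleeding bullet lists drop-out and loss to follow-up, together with deaths unrelated to bleeding, as both non-event and censored. The mortality bullet asks for a K-M rate and a descriptive rate at 6 and 12 months and then applies the non-event rule without saying which of the two it governs.

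Section 7.3.2 does the same for post-thrombotic syndrome (PTS): "Early drop out, lost-to-follow-up and death will be considered as non-event and censored". The descriptive rate is tied explicitly to 6 and 12 months for mortality and PTS. For VTE and bleeding the time points come from the endpoint definitions in section 5.2.1.

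Section 7.4 says that "Missing data will not be imputed in general" and that patients are followed after stopping study drug. The current text does not say when the analysis takes place relative to the last 12-month visit. The log for global amendment 07 in section 11 records that such a condition was deleted from section 7.3.

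**The concern.** With all treated patients in the denominator, scoring an unknown outcome as a non-event is a fixed assumption in the favourable direction. The result equals the true risk if nobody is lost and falls below it otherwise. Sections 7.1 and 7.2 describe a single group, no control and no hypothesis test, so the absolute rates are the result of the trial and no comparison between arms can offset the bias.

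Patients still under observation at the data cut raise the same problem. They have been treated, so they enter the denominator, and until they have an event they cannot enter the numerator.

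The report could then carry two different 12-month figures for the same endpoint, one of which is too low in a known direction.

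**Working it through.** **Inputs from the protocol.** At least 100 patients and a 12-month rate of 5% for the composite in section 7.6 (recurrent VTE, major bleeding, thromboembolic death), used here as an illustrative risk. The descriptive rate is events over all treated patients (section 7.3.1).

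**Inputs assumed.** The protocol gives no drop-out rate, so 10%, 20% and 30% by 12 months are shown. Event and drop-out hazards are constant and independent.

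**The plan's own figures.** The probability of at least one event in 100 patients is 1 − 0.95^100 = 99.4% at a 5% rate and 1 − 0.99^100 = 63.4% at 1%. Both agree with section 7.6. The 95% Wilson interval for 5 of 100 is 2.15% to 11.18%, in line with Table 7.6:1.

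**Step 1: descriptive rate under drop-out.** Let p be the true 12-month risk and d the drop-out by 12 months, with λ = −ln(1 − p) and μ = −ln(1 − d). The expected descriptive rate is

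crude = λ/(λ + μ) × [1 − exp(−(λ + μ))].

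For p = 5%, λ = 0.0513. At d = 20%, μ = 0.2231 and exp(−(λ + μ)) = 0.95 × 0.80 = 0.76, so crude = 0.0513/0.2744 × 0.24 = 4.49%.

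| Drop-out by 12 months | Descriptive rate, 12 months (true 5%) | Relative shortfall | Descriptive rate, 6 months (true 2.53%) |
|---|---|---|---|
| 0% | 5.00% | 0% | 2.53% |
| 10% | 4.75% | 5% | 2.47% |
| 20% | 4.49% | 10% | 2.40% |
| 30% | 4.21% | 16% | 2.32% |

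If all losses occurred at day 0, the 12-month figure would be 5% × (1 − d), which is 4.0% at d = 20%.

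**Step 2: the planned K-M rate under the same assumptions.** Simulation with 100 patients and 20,000 replicates gives average 12-month K-M rates of 5.03%, 5.01% and 5.01% at 10%, 20% and 30% drop-out. There is no understatement.

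**Step 3: analysis with patients still on study.** Let a fraction g have follow-up uniform over 0 to 12 months, with nobody lost. Then

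crude = (1 − g) × p + g × [1 − (1 − exp(−λ))/λ].

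The bracket is 1 − 0.05/0.0513 = 2.52%. For g = 0.5, crude = 0.5 × 5% + 0.5 × 2.52% = 3.76%, about 25% too low. For g = 0.25 it is 4.38%, about 12% too low.

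**Step 4: a tempting repair.** Suppose the denominator is restricted to patients with the event or with complete follow-up. The expected rate becomes crude/[crude + 0.95 × (1 − d)]. At d = 20% this is 0.0449/(0.0449 + 0.76) = 5.57%. At 10% and 30% it is 5.26% and 5.96%. The error is about as large as before, with the opposite sign.

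**The case against.** The strongest reply is that the plan already contains the right estimator. Kaplan-Meier with censoring is the main summary and the descriptive rate is an addition. A reader might infer from the non-event rule that all primary safety results are understated. The documents do not support this: section 7.3.1 gives K-M rates at 6 and 12 months, and Step 2 shows that they hold under non-informative censoring. Informative drop-out could bias them, but that is a separate question and does not come from this rule.

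Three further replies carry weight.

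- **Stopping drug is not dropping out.** Sections 3.1, 3.3.4.1, 6.2.3 and 7.4 keep such patients under follow-up, and sites must try to locate lost patients about every three months. This reduces the loss but does not remove it. Section 6.2.3 allows follow-up for vital status only, which leaves VTE, bleeding and PTS unknown. The flow chart schedules PTS evaluation only at Visits 8 and 11, so a patient lost before Visit 8 has had no scheduled PTS assessment, yet counts as free of it.
- **The size is modest.** At 10% to 30% drop-out the shortfall is 0.25 to 0.79 percentage points, less than one patient in 100 and small beside the interval of 2.15% to 11.2% in Table 7.6:1.
- **Section 7.4 is not really contradicted.** It rules out imputation only in general, and 7.3.1 states a specific counting rule.

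A reader might also take the reference in the VTE bullet to events up to the time of analysis as proof that patients short of month 12 are to be scored event-free. That sentence is the K-M rule, and it censors them. The early-cut problem rests instead on the all-treated denominator and on the absence of a fixed analysis time. The current text permits such a cut but does not plan one. Nor does the protocol say that the descriptive rate will be the figure quoted.

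**Conclusion.** The point holds for the supplementary descriptive rates of VTE, bleeding, mortality and PTS. They are lower bounds, below the true risk whenever outcomes are unknown. It does not hold for the planned K-M rates.

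For a true 12-month risk of 5% the relative shortfall is about 5%, 10% or 16% at 10%, 20% or 30% drop-out, and about 25% if half the patients are only part-way through follow-up at the cut. These sizes rest on constant hazards, non-informative drop-out and assumed amounts of incomplete follow-up. With complete follow-up the shortfall is zero. The direction needs no such assumption, because a missed event can only lower the count.

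The wording needs a lesser correction. Only the VTE bullet confines the non-event rule to the descriptive rate. The general paragraph of 7.3.1 makes clear that drop-outs are censored in the K-M analysis, but the bleeding, mortality and PTS bullets can be read as applying both rules at once.

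The matter is worth correcting because the rule is explicit, its bias favours the product in a trial without a control, and the better figure is already planned.

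**What to change.** In sections 7.3.1 and 7.3.2:

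1. Delete the non-event rule for the 6- and 12-month rates and take those risks only from the time-to-event estimate, with 95% CI.
2. Replace the crude ratio with events per 100 patient-years, which uses each patient's actual follow-up.
3. If patients with event over all treated is kept, label it as the observed proportion, a lower bound and not a 6- or 12-month risk. Show beside it the number without complete follow-up at each time point.
4. State in the bleeding, mortality and PTS bullets that drop-outs and lost patients are censored in the K-M analysis.
5. Do not restrict the denominator to patients with the event or complete follow-up, since that overstates the risk (Step 4).

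The cost is a few sentences and a little more analysis work, with no new data. The reported figures will be slightly less favourable.
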